Appendix 5 Clinical Laboratory Tests

The protocol-required clinical laboratory assessments are in the following table:

Laboratory Assessments	Parameters			
Hematology	Platelet count		Mean corpuscular volume (MCV)	White Blood Cell Count with Differential: Neutrophils Lymphocytes Monocytes Eosinophils Basophils
	Hemoglobin		Mean corpuscular hemoglobin (MCH)	
	Hematocrit			
Biochemistry	Blood Urea Nitrogen	Potassium	Aspartate aminotransferase	Total Bilirubin
	Creatinine	Sodium	Alanine aminotransferase	Total Protein
	Glucose	Calcium	Alkaline phosphatase	Albumin
	Uric acid	Chloride	Gamma-glutamyl transferase	Cholesterol
		Inorganic phosphate	Lactate dehydrogenase	Triglycerides
		Magnesium	Creatinine phosphatase	Amylase
				Lipase
Routine Urinalysis	Specific gravity pH, glucose, protein, blood (hemoglobin), ketones, bilirubin, urobilinogen, nitrite, leukocyte esterase by dipstick Microscopic examination (if blood or protein is abnormal with positive dipstick). Note: In case of a positive result for hemoglobin, leukocyte esterase, protein or nitrite, a flow cytometry count and classification will be performed.			
Coagulation	
 International normalized ratio Activated partial thromboplastin time 			
Other Screening Tests	
 Follicle stimulating hormone (at Screening only) Urine drug screen (to include at minimum: amphetamines, methamphetamines, barbiturates, ecstasy, cocaine, opiates, cannabinoids, benzodiazepines, methadone, phencyclidine, oxycodone, and tricyclic antidepressants, Screening and Day -1) Serology (human immunodeficiency virus I and II antibodies, hepatitis B surface antigen, hepatitis B core antibody, hepatitis C antibody, QuantiFERON test) SARS-CoV-2 test (Screening and Day -1) Note: According local regulations at the time of study conduct. Thyroid stimulating hormone (at Screening only) Cotinine test (Screening and Day -1) Alcohol breath test (Screening and Day -1) Estimated Glomerular Filtration Rate based on Chronic Kidney Disease Epidemiology Collaboration Creatinine Equation (2009) Presence of HLA-B* 1502 or HLA-A* 3101 (Screening) 
All study-required laboratory assessments will be performed by a central laboratory (Nuvisan's clinical laboratory) apart from analysis of HLA-B* 1502 or HLA-A* 3101 which will be performed by another vendor with these assessment capabilities.
			

HLA-A=human leucocyte antigen A, HLA-B= human leucocyte antigen B, SARS-CoV-2=severe acute respiratory syndrome coronavirus type 2.

Appendix 7 Examples of Inhibitors or Inducers of CYP3A Enzymes or Substrates with Narrow Therapeutic Range

Inhibitors		
Strong ^a	Moderate ^b	Weak ^c
Boceprevir, clarithromycin, conivaptan, grapefruit juice ^d , indinavir, itraconazole, ketoconazole, lopinavir/ritonavir, mibefradil, nefazodone, neflifavir, posaconazole, ritonavir, saquinavir, telaprevir, telithromycin, and voriconazole	Amprenavir, aprepitant, atazanavir, ciprofloxacin, darunavir/ritonavir, diltiazem, erythromycin, fluconazole, fosamprenavir, grapefruit juice ^a , imatinib, and verapamil	Alprazolam, amiodarone, amlodipine, atorvastatin, bicalutamide, cilostazol, cimetidine, cyclosporine, fluoxetine, fluvoxamine, ginkgo, goldenseal, isoniazid, nilotinib, oral contraceptives, ranitidine, ranolazine, tipranavir/ritonavir, and zileuton
Inducers		
Strong ^a	Moderate ^b	Weak ^c
Avasimibe, carbamazepine, phenytoin, rifampin, and St. John's wort	Bosentan, efavirenz, etravirine, modafinil, and naftilin	Amprenavir, aprepitant, armodafinil, echinacea, pioglitazone, prednisone, and rufinamide
Substrates With a Narrow Therapeutic Range		
Alfentanil, astemizole ^e , cisapride ^e , cyclosporine, dihydroergotamine, ergotamine, fentanyl, pimozide, quinidine, sirolimus, tacrolimus, terfenadine ^e		

CYP=cytochrome P450.

Sources: This is not an exhaustive list. For an updated list, see the following links:

<https://www.fda.gov/drugs/drug-interactions-labeling/drug-development-and-drug-interactions-table-substrates-inhibitors-and-inducers#table2-2>.<https://www.fda.gov/drugs/drug-interactions-labeling/drug-development-and-drug-interactions-table-substrates-inhibitors-and-inducers#table2-3>.<https://www.fda.gov/drugs/drug-interactions-labeling/drug-development-and-drug-interactions-table-substrates-inhibitors-and-inducers#table3-2>.<https://www.fda.gov/drugs/drug-interactions-labeling/drug-development-and-drug-interactions-table-substrates-inhibitors-and-inducers#table3-3>.

Note: CYP substrates with narrow therapeutic range refers to drugs whose exposure-response relationship indicates that small increases in their exposure levels by the concomitant use of CYP inhibitors may lead to serious safety concerns (e.g., Torsades de pointes).

- a: A strong inhibitor is defined as an inhibitor that increases the AUC of a substrate sensitive for that CYP \geq 5-fold or decreases clearance by $> 80\%$, and a strong inducer decreases AUC of a substrate by $\geq 80\%$.
- b: A moderate inhibitor is defined as an inhibitor that increases the AUC of a substrate sensitive for that CYP \geq 2-fold but < 5 -fold or decreases clearance by 50% to 80%, and a strong inducer decreases AUC by 50% to 80%.
- c: A weak inhibitor is defined as an inhibitor that increases the AUC of a sensitive substrate for that CYP < 2 -fold or decreases clearance 20% to 50%, and a weak inducer decreases AUC by 20% to 50%.
- d: The effect of grapefruit juice varies widely among brands and is concentration, dose, and preparation dependent. Studies have shown that it can be classified as a “strong CYP3A inhibitor” when a certain preparation is used (e.g., high dose, double strength) or as a “moderate CYP3A inhibitor” when another preparation is used (e.g., low dose, single strength).
- e: Withdrawn from the US and certain other markets because of safety reasons.

TLF	Tables, Listings, and Figures
UCI	Upper Limit of Confidence Interval

3

Modification History

Unique Identifier for Version	Date of IAP Version	Author	Changes from the Previous Version
Final 1.0	23-Feb-2022	PPD	Initial version.

4

Purpose of the Integrated Analysis Plan

The purpose of this IAP is to document technical and detailed specifications for the final analysis of data collected for protocol MS200527_0108. Results of the analyses described in this IAP will be included in the CSR. Additionally, the planned analyses identified in this IAP may be included in regulatory submissions or future manuscripts. Any post-hoc, or unplanned analyses performed to provide results for inclusion in the CSR but not identified in this prospective IAP will be clearly identified in the CSR.

The IAP is based upon Section 9 (Statistical considerations) of the study protocol and protocol amendments and is prepared in compliance with ICH E9. It describes analyses planned in the protocol and protocol amendments.

The wording used in this IAP is chosen to best match the respective wording in the study protocol template, the CSR template, CDISC requirements and special requirements for table layouts. Therefore, the following approach is used:

Generally, the term ‘participant’ will be used instead of ‘subject’ or ‘patient’. However, in tables and listings the term ‘subject’ will be used to match CDISC requirements, except for in-text tables where ‘participant’ will be used to match the CSR and protocol templates. Similarly, the term ‘study intervention’ will be used in this document instead of ‘treatment’ to match protocol and CSR templates, however, tables and listings will use ‘treatment’ for brevity reasons. Exceptions from this rule are commonly used terms like “on-treatment”, “treatment-emergent”, “treatment policy”, “subject-years”, “by-subject”, or names of eCRF pages like “Treatment Termination” page.

5 Objectives and Endpoints

Objectives	Endpoints	Ref #
Primary		
To investigate the effect of multiple doses of carbamazepine on the PK of a single dose of evobrutinib in healthy participants	
 Plasma evobrutinib: $AUC_{0-\infty}$ Plasma evobrutinib: C_{max} 	1
Secondary		
To assess the safety and tolerability of evobrutinib when administered together with carbamazepine in healthy participants	
 Nature, occurrence, severity, and seriousness of TEAEs Absolute values and changes in safety laboratory tests from time of first dose to end of study participation Single 12-lead ECGs evaluated by Investigator from time of first dose to end of study participation Vital signs assessed from time of first dose to end of study participation 	2
To characterize the effect of carbamazepine on additional evobrutinib PK parameters in healthy participants	
 Plasma evobrutinib: CL/F Plasma evobrutinib: V_z/F Plasma evobrutinib: $AUC_{0-t_{last}}$ Plasma evobrutinib: t_{max} Plasma evobrutinib: $t_{1/2}$ 	3
To characterize the effect of carbamazepine on evobrutinib metabolite (MSC2729909A) PK in healthy participants	
 Plasma MSC2729909A: $AUC_{0-\infty}$ Plasma MSC2729909A: $AUC_{0-t_{last}}$ Plasma MSC2729909A: C_{max} Plasma MSC2729909A: t_{max} Plasma MSC2729909A: $t_{1/2}$ Plasma MSC2729909A: metabolite to parent ratios $M/P(AUC_{0-\infty})$ and $M/P(C_{max})$ 	4
CCI		
	  	
	  	
	  	

AUC=area under the concentration-time curve; C_{max} =maximum observed concentration; C_{min} = minimum observed concentration; CL/F =apparent total body clearance; ECG=electrocardiogram; M=metabolite; P=parent; PK=pharmacokinetics; TEAE=treatment emergent adverse event; $t_{1/2}$ =apparent terminal half-life; t_{lag} =time prior to the first measurable (nonzero) concentration; t_{max} =time to reach the maximum observed concentration; V_z/F =apparent volume of distribution.

6 Overview of Planned Analyses

The final, planned analyses identified in the CSP and in this IAP will be performed after the last participant has completed the last visit and after all data queries resolved as well as the database locked.

A data review meeting will be held prior to database lock for the final analysis. In addition, no database can be locked until this IAP has been approved.

7 Changes to the Planned Analyses in the Clinical Study Protocol

An interim data review may occur if necessary for data evaluation in order to make decision on the dosing of subjects. In that case, an unplanned interim analysis request form will be submitted for approval to the Head of GBS and the decision will be thoroughly documented.

8 Analysis Sets and Subgroups

8.1 Definition of Analysis Sets

Analysis Set	Description
SCR	All participants, who provided informed consent, regardless of the participant's enrollment and study intervention status in the study.
SAF	All participants, who were administered any dose of any study intervention. Analyses will consider participants as treated.
PK	The PK Analysis Set is a subset of the SAF, and the PK population will include all participants: Who have completed the study without any relevant protocol deviations and factors likely to affect the comparability of PK results. With adequate study intervention compliance. With evaluable PK data, i.e., nonmissing values for primary endpoints. If participants received prohibited concomitant therapy or medicines, as specified in Section 6.8 of the CSP, they will be excluded from the PK population. All PK analyses will be based on this analysis set.

PK=pharmacokinetics; SAF=safety; SCR=Screening.

8.2 Subgroup Definition and Parameterization

Not applicable.

9 General Specifications for Data Analyses

The results of this study will be reported using summary tables, figures, and data listings, as appropriate. All data will be summarized by study intervention and/or scheduled time point, as applicable.

Listings

In the individual participant data listing all individual data will be listed as measured. Repeated and unscheduled measurements will be included in the listings. All listings will be sorted by subject ID and nominal time point, if not stated otherwise.

Tables and Descriptive Statistics

All safety data will be summarized overall by nominal time point, as appropriate. All PK data will be summarized by study intervention and nominal time point. Repeated and unscheduled measurements included in the listings will not be used for statistical analyses or summaries, unless the repeated measurement was performed due to unreliable values/technical reasons, e.g., clotted samples.

Unless otherwise specified, continuous variables will be summarized using descriptive statistics, i.e. the number of participants with non-missing values (n), the number of participants with missing values (nmiss), mean, standard deviation, median, 25th percentile (Q1) and 75th percentile (Q3), minimum, and maximum. If there are no missing values the number of participants with missing values should be indicated by a 0. Mean, Median, Q1, Q3, Min, Max will have the same precision as the SDTM data (decimal places). SD will be presented with one decimal place more than the mean.

Qualitative variables will be summarized by frequency counts and percentages. Unless otherwise stated the calculation of proportions will be based on the number of participants of the analysis set of interest that received the respective study intervention for AE and PK tables and for all other evaluations the analysis set of interest [N]. Therefore, counts of missing observations will be included in the denominator and presented as a separate category.

Study day 1 for this study is defined as the start date of study intervention.

The following labels will be used for the study interventions in PK tables and listings, if not stated otherwise:

Evobrutinib: 45 mg Evobrutinib on Day 1

Carbamazepine+Evobrutinib: Carbamazepine from Day 2 to Day 25 plus 45 mg Evobrutinib on Day 19

All statistical analyses will be performed using SAS® Software version 9.2 or higher.

9.1 Definition of Baseline and Change from Baseline

If not otherwise specified, 'baseline' refers to the last scheduled measurement before administration of study intervention.

However, if a participant is missing the baseline collection, the previous non-missing evaluation could become the baseline value (e.g. from Screening). If no baseline or previous to baseline evaluations exist, then the baseline value will be treated as missing.

Absolute changes from baseline are defined as

$$\text{absolute change} = \text{visit value} - \text{baseline value}$$

9.2 Study Day / Study Intervention Day

Day 1 is the day of start of study intervention, the day before is Day -1 (no Day 0 is defined). Study day is defined relative to Day 1.

9.3 Definition of Duration and ‘Time Since’ Variables

The following definitions and calculations of duration, as applicable, will be applied:

- Duration of AE (in days hh:mm) = end date and time - start date and time of the AE, if missing time for either the beginning or end then = end date – start date + 1; in case of multiple records for the same AE, the duration will be calculated over all these records
- Days hh:mm from dosing (onset post administration) = start date and time of the event - date and time of last dose administration of cocktail, evobrutinib or sumatriptan (calculated for each intervention, for TEAEs), if missing time for either the dosing or event then days hh:mm from dosing = event start date – date of dose administration + 1
- Relative (Rel.) Day in study of AE = start date of the event – date of first admin + 1 (for AEs on or after the day of dosing)
- Rel. Day in study of AE = start date of the event – date of first admin (for events before the day of dosing of the study only)

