5.3 Lifestyle Considerations

5.3.1 Meals and Dietary Restrictions

Abstain from consumption of the following from 14 days before the start of study intervention until after the final dose: Seville oranges, grapefruit or grapefruit juice, pomelos, exotic citrus fruits, grapefruit hybrids, and their juices.

On Day 1 and Day 19, participants will receive a single dose of 45 mg evobrutinib (tablets) after overnight fasting for at least 10 hours in the morning 0.5 hours after the start of a standard moderate-fat/moderate-calorie breakfast at the CRU. The breakfast should be consumed within 25 to 30 minutes. The start date and time and stop time of the breakfast will be recorded in the participant's eCRFs as well as whether the entire breakfast was consumed. If the entire meal is not consumed, the percentage of meal consumed (in quartiles) should be recorded.

Standard moderate-fat, moderate-calorie breakfasts on evobrutinib dosing days are defined as follows: 490 calories composed of approximately 77 g of carbohydrates, 28 g of protein, and 13 g of fat (Naderer 2015).

All other meals during the inpatient stay at the study center will be standardized and no documentation of time and complete consumption is needed.

On Days 2 to 19, each participant will receive 100, 200 or 300 mg carbamazepine (tablets) twice daily (at least 10 hours apart) during, after, or between meals at the CRU at approximately the same time each day. On Day 19, in the morning, carbamazepine will be co-administered with evobrutinib. The morning carbamazepine dose on Day 20 will be administered at the CRU prior to participants' release from the CRU. Once in the evening of Day 20 and twice daily on Days 21 to 25, participants will take carbamazepine at home.

Study interventions will be administered with 240 mL of water in a standing position at the CRU. On all dosing days (Schedule of Assessments in Section 1.3), participants may consume water ad libitum and should drink at least 1.5 L/day.

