6.1 Study Intervention(s) Administration

Intervention Name	Evobrutinib	Carbamazepine
Type	Drug	Drug
Dose Formulation	Film-coated tablet (TF2)	Tablet with break-line
Unit Dose Strength(s)	45 mg	200 mg (0.5, 1.0 and 1.5 tablet[s])
Dose Amount	45 mg, fed	100 mg (Days 2 and 3), 200 mg (Days 4 and 5), 300 mg (Days 6 to 19), 200 mg (Days 20 to 22) and 100 mg (Days 23 to 25) per administration, fed
Frequency	Single dose on Day 1 and Day 19	Twice daily at the same time each day in the morning and evening (at least 10 hours apart, \pm 1 hour) from Days 2 to 25

Route of Administration	Oral	Oral
Use	Experimental	Experimental
Investigational Medicinal Product	Evobrutinib	Carbamazepine
Supplier	Merck Healthcare KGaA	Merck Healthcare KGaA
Packaging and Labeling	Study intervention will be provided in containers. Each container will be labeled per country requirement. Additional details of packaging and labeling of study intervention will be defined in a separate IMP Handling Manual.	Study intervention will be provided in containers. Each container will be labeled per country requirement. Additional details of packaging and labeling of study intervention will be defined in a separate IMP Handling Manual.

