6.4 Study Intervention Compliance

When participants are dosed at the site, they will receive study intervention directly from the Investigator or designee, under medical supervision. The date and time of each dose administered in the clinic will be recorded in the source documents and recorded in the CRF. The dose of study intervention and study participant identification will be confirmed at the time of dosing by a member of the study site staff other than the person administering the study intervention. Study site personnel will examine each participant's mouth to ensure that the study intervention was ingested.

When participants self-administer study intervention(s) at home, compliance with study intervention will be assessed at each visit. Compliance will be assessed by a participant diary during the site visits and documented in the source documents and CRF. Any deviation(s) from the prescribed dosage regimen are recorded in the CRF. Note: In this study, compliance with carbamazepine intake at home will be assessed at the Safety Follow-Up Visit only.

A record of the number of carbamazepine tablets dispensed to and taken by each participant will be maintained and reconciled with study intervention and compliance records. Intervention start and stop dates, including dates for intervention delays and/or dose reductions will also be recorded in the CRF.

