11.3 Other Baseline Characteristics

Other baseline measurements, such as virus screen, alcohol and drugs of abuse screen, pregnancy test in women, nicotine, and alcohol consumption, will be listed.

Baseline characteristics with respect to vital signs, physical examinations, and hematology/biochemistry will be part of Section 15 (Safety Evaluation).

12 Previous or Concomitant Therapies/Procedures

Medications will be presented for the Safety Analysis Set.

Previous medications are defined as any medication discontinued prior to the administration of study intervention. Concomitant medications are defined as any medication taken during the course of the study, with a starting date greater than or equal to the administration of study intervention, or with a starting date prior to the administration of study intervention and ongoing at the time of the administration of study intervention.

The World Health Organization Drug dictionary most current version at time of database lock, will be used for coding of prior and concomitant medications and they will be described using PT as applicable.

Previous and concomitant medications will be listed. Concomitant procedures, if any, will also be listed.

13 Study Intervention: Compliance and Exposure

The dosing of each participant is monitored by the study nurse or investigator. A listing of date and time of each drug administration and each blood sampling, including time deviations as well as measured plasma concentrations, will be provided sorted by participant. Information on meal intake will be listed by participant, if provided.

14 Efficacy Analyses

Not applicable.

15 Safety Analyses

This section includes specifications for summarizing safety endpoints that are common across clinical studies such as adverse events, laboratory tests and vital signs.

All safety analyses will be performed for the Safety Analysis Set and will be presented overall by nominal timepoint, as appropriate.

Safety analyses will be done according to the as-treated principle.

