15.1.1 All Adverse Events

TEAEs and participants experiencing TEAEs will be summarized overall with:

- The number and percentage of participants with any TEAE, any related TEAE, any evobrutinib-related TEAE, any carbamazepine-related TEAE, any serious TEAE, any related serious TEAE, any evobrutinib-related serious TEAE, any carbamazepine-related serious TEAE, any severe TEAE, any related severe TEAE, any evobrutinib-related severe TEAE, any carbamazepine-related severe TEAE, any AESI, any TEAE leading to death, any related TEAE leading to death, any evobrutinib-related TEAE leading to death, any carbamazepine-related TEAE leading to death, any TEAE leading to study discontinuation
- The number and percentage of participants with at least one TEAE and the number of events by SOC and PT.
- The number and percentage of participants with TEAEs excluding SAEs and the number of events, with frequency $\geq 5\%$ in any study intervention arm by SOC and PT
- The number and percentage of participants with at least one TEAE and the number of events by severity, SOC, and PT

- The number and percentage of participants with at least one related TEAE, evobrutinib-related TEAE, carbamazepine-related TEAE and the number of events by SOC and PT
- The number and percentage of participants with at least one AESI recorded and the number of events by SOC and PT.

Unless otherwise stated, AEs will be displayed with SOC terms sorted alphabetically and PTs within each SOC term sorted in descending overall frequency.

For determining incidence counts, within each level of TEAE term, if a participant experiences more than one occurrence, the participant will only be counted once for that TEAE.

AEs related to any study intervention are those events with relationship missing, unknown or yes.

In case a participant had events with missing and non-missing severity, the maximum non-missing severity will be displayed.

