15.1.2 Adverse Events Leading to Discontinuation of Study Intervention

A listing of TEAEs leading to discontinuation of study intervention, or discontinuation of study, if any, will be provided.

The frequency (number and percentage) of participants with TEAEs leading to permanent discontinuation of each study intervention by study intervention will also be provided in a table.

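### Does the onset-since-dose rule in SAP 9.3 need correcting, given that it names two products not used in this trial and omits carbamazepine?

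*SAP*

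**What the plan says.** SAP 9.3 lists the duration and time-since variables for adverse events. For TEAEs, days and hours from dosing are the event start minus the "date and time of last dose administration of cocktail, evobrutinib or sumatriptan (calculated for each intervention, for TEAEs"). When a clock time is missing, a date-only rule applies: "if missing time for either the dosing or event then days hh:mm from dosing = event start date – date of dose administration + 1". That fallback names no product.

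Protocol 6.1 lists two study interventions. Evobrutinib is a single dose on Day 1 and again on Day 19. Carbamazepine is given from Day 2 to Day 25, "Twice daily at the same time each day in the morning and evening". The intervention labels in SAP Section 9 use the same two drugs and no others.

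Elsewhere the SAP treats carbamazepine as an intervention in its own right. Section 15.1.1 plans "The number and percentage of participants with at least one related TEAE, evobrutinib-related TEAE, carbamazepine-related TEAE and the number of events by SOC and PT". Section 15.1.2 says that the frequency of "participants with TEAEs leading to permanent discontinuation of each study intervention by study intervention will also be provided in a table". Section 13 promises "A listing of date and time of each drug administration and each blood sampling, including time deviations".

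**The concern.** The rule names two products that no participant receives and leaves out the drug that participants take on most study days. Removed text does not explain this: the intervention table in Protocol 6.1 is complete, and the protocol title names only evobrutinib and carbamazepine. The SAP is its initial final version, so the sentence is not superseded wording either. It reads as text carried over from another study's plan, though that is an inference.

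If the rule were programmed as written, time since the last carbamazepine dose would have no definition for any TEAE. A reader of the adverse event data who wanted to see how soon an event followed carbamazepine would find only the time since evobrutinib. Relative study day does not fill the gap, because it counts from the first administration and not from the latest dose. Since the SAP reports carbamazepine-related events separately, a reader could reasonably expect onset timing for both drugs.

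**Working it through.** There is no sample size, power or model figure to reproduce. The check sets the text side by side and adds some counting.

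**1. Share of dosing that the rule names.** Protocol 2.3 gives 18.5 days of twice-daily carbamazepine in the clinic and 5.5 days at home.
- In clinic: 18.5 × 2 = 37 administrations.
- At home: 5.5 × 2 = 11 administrations.
- Total carbamazepine: 37 + 11 = 48, which agrees with Days 2 to 25, 24 × 2 = 48.
- Evobrutinib: 2.
- All administrations: 48 + 2 = 50. Read literally, the rule covers 2 of 50.

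**2. What the literal rule returns.**
- From the first carbamazepine dose on Day 2 to the Day 19 evobrutinib dose: between 2 − 1 = 1 and 19 − 1 = 18 days since evobrutinib.
- From Day 19 to the Day 26 visit: up to 26 − 19 = 7 days since evobrutinib.
- Example with a missing clock time, onset on Day 10: 10 − 1 + 1 = 10 days from evobrutinib. With carbamazepine taken that day, the same fallback would give 10 − 10 + 1 = 1 day.

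**3. Size of the value left undefined.** Protocol 5.3.1 has carbamazepine given "twice daily (at least 10 hours apart) during, after, or between meals at the CRU at approximately the same time each day". With two doses a day at least 10 hours apart, the longest scheduled gap is 24 − 10 = 14 hours. Protocol 6.1 adds a tolerance of 1 hour without saying what it applies to. If it shortens the minimum spacing to 9 hours, the longest gap is 24 − 9 = 15 hours. If each of the two doses may drift by 1 hour, it is 14 + 2 = 16 hours. During in-clinic dosing the missing value is therefore at most about 14 to 16 hours.

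**4. What uses the variable.**
- *TEAE status* (SAP 15.1): onset on or after the first administration on Day 1. Not used.
- *Relatedness* (Protocol Appendix 4; SAP 15.1.1): the investigator's causality assessment, with a separate SAP rule for missing relatedness. Not used.
- *Duration and relative day* (SAP 9.3): each has its own formula. Not used.
- *Tables in SAP 15.1 and 15.2*: counts of participants and events by class, term, severity, relatedness and discontinuation. Not used.
- *Adverse event listings* (SAP 15.1): planned, but no column for this variable is specified.
- *Pharmacokinetic comparison* (SAP 16.1.3): Day 19 against Day 1 on log-transformed parameters. Not used.

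**5. Whether an analyst could go wrong.** The sentence asks for a value for each intervention. Protocol 6.1 and SAP Section 9 give two interventions. The dosing data will hold no cocktail or sumatriptan records, so the derivation prompts the question itself, and carbamazepine is the only answer available.

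**The case for a change.** The strongest case for a correction is that an analysis plan exists to fix technical detail. A closed list of three products does not gain a fourth because a parenthesis asks for the value per intervention. If the programmer quietly substitutes carbamazepine, the code and the plan disagree on paper. The repair would be one line, and Protocol 6.4 already secures most of the data: "The date and time of each dose administered in the clinic will be recorded in the source documents" and in the CRF.

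The textual part of this stands. The list is wrong, and those words do not literally add the missing drug.

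Two supporting arguments are weaker. SAP 15.1.1 and 15.1.2 do not conflict with 9.3. Their tables can be produced in full with 9.3 as it is; they show only that the omission was unintended. Nor would a one-line swap settle every case. Protocol 6.4 assures dates and times for doses given in the clinic. For the 11 home doses, from the evening of Day 20 to Day 25, it describes a diary-based compliance check at the Safety Follow-Up visit, recorded deviations and tablet counts. It does not say that the date of each home dose enters the CRF, and the date-only fallback needs that date. Analysts would still have to make a working assumption for late events, with or without the correction.

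**Conclusion.** This is a genuine clerical slip with no consequence that calls for a change to the plan. The evobrutinib interval is correctly defined. The carbamazepine interval is not, but it feeds no named table, no classification of events and no pharmacokinetic result. Where someone wants it for an event during in-clinic dosing, it is at most about 14 to 16 hours and can be worked out from the administration listing in SAP Section 13.

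The conclusion rests on two assumptions. The first is that no output beyond those named in the SAP relies on this variable; none is specified in the visible text. The second is that the programmer, finding no records for the two stray products, reads the rule as covering the two drugs actually given. That is very likely, because the trial has no other interventions. The documents give no basis for estimating how many events would fall in the affected window, but no reported count or estimate would differ whatever that number is.
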